## 9 Selection of Clinical Investigation Population

Subjects participating in this clinical investigation will be recruited from the investigator's standard subject population, where all neuropathic subjects presenting for treatment of deformity will be evaluated for clinical investigation participation based on the eligibility criteria listed below.

### 9.1 INCLUSION CRITERIA

- a. Subject is a male or non-pregnant female age 18 years or older at the time of surgery;
- b. Subject is willing and able to give written informed consent and comply with the requirements of this Clinical Investigation Plan (CIP); and
- c. Subject has neuropathy and is intended to be treated for deformity with the one or a combination of the below Systems in accordance with the legally cleared/ approved IFU and Surgical Technique Manual.
  - HOFFMANN® LRF SYSTEM
  - SALVATION™ EXTERNAL FIXATION SYSTEM
  - SALVATION™ FUSION BOLTS AND BEAMS
  - SALVATION™ 2 MIDFOOT NAIL
  - SALVATION™ 3DI PLATING SYSTEM

- T2® ICF SYSTEM
- VALOR™ ANKLE FUSION NAIL SYSTEM

## 9.2 EXCLUSION CRITERIA

- a. Subjects determined, by the investigator, to be an inappropriate candidate for the procedure indicated;
- b. Unable to consent to participate (written, informed consent);
- c. Unable to attend/complete the requested follow-up visits

## 9.3 POINT OF ENROLLMENT

Subjects will be considered enrolled in the study when they have satisfied all the below:

- a. Been informed of all aspects of the study and have signed Informed Consent document
- b. Acknowledged the appropriate patient data release information (included in the Informed Consent document)
- c. Satisfied the Inclusion/Exclusion Criteria
- d. Implanted with HOFFMANN® LRF SYSTEM, SALVATION™ EXTERNAL FIXATION SYSTEM, SALVATION™ FUSION BOLTS AND BEAMS, SALVATION™ 2 MIDFOOT NAIL, SALVATION™ 3DI PLATING SYSTEM, T2® ICF SYSTEM, and/or VALOR™ ANKLE FUSION NAIL Systems.

Investigators should document subject enrollment in the electronic data capture system. The Source documentation should clearly state that all inclusion and exclusion criteria have been met and the patient data release and informed consent documents have been signed and appropriately dated prior to any study related activity. The subject is enrolled in the study once they have received the study device.

## 9.4 WITHDRAWAL CRITERIA

If, during the clinical investigation, a subject must be prematurely withdrawn, the procedures outlined in this section must be followed. These procedures should not interfere with the initiation of any new treatments that are necessary to treat a subject's condition. Information on all withdrawn subjects will be documented.

Subjects may be withdrawn from the clinical investigation for any of the following reasons:

- a. Subject Withdrawal: A subject may voluntarily withdraw from the clinical investigation at any time and for any reason. The subject should be asked when possible, and without any form of coercion, the reason for his/her decision. If the participant withdraws from the clinical investigation completely, then data collected up until the point of withdrawal will be included in the final analysis. Subjects who decline to continue to take part will be given the opportunity to discuss/inform the research team of the reasoning behind their decision not to take part.
- b. Lost to Follow-Up (LTFU): A subject will be considered LTFU after all reasonable efforts have been made to contact the subject and request his/her continued participation in the clinical investigation. All attempts to contact the subject must be documented and should include at least two attempts to contact the subject by phone and one attempt via a certified letter. Data collected up until the point where the subject is LTFU will be included in the final analysis.

- c. Amputation: The discontinuation of a subject's participation in the clinical investigation due to Amputation (below the knee or above the knee) All available information concerning the amputation AEs should be provided. Data collected up until the point of amputation will be included in the final analysis.
- d. Adverse Event: The discontinuation of a subject's participation due to an AEs that prohibits his/her continued participation must be fully explained. All available information concerning the AEs should be provided. Data collected up until the point of AE will be included in the final analysis.
- e. Death: The discontinuation of a subject's participation in the clinical investigation due to death must be fully explained. All available information concerning the death should be provided. Removal of a subject from continued follow-up in the clinical investigation due to death will not be considered a device failure unless the death is directly caused by, or attributable to, the HOFFMANN® LRF CIRCULAR EXTERNAL FIXATION, SALVATION™ EXTERNAL FIXATION SYSTEM, SALVATION™ FUSION BOLTS AND BEAMS, SALVATION™ 2 MIDFOOT NAIL, SALVATION™ 3DI PLATING SYSTEM, T2® ICF INTRAMEDULLARY NAILING SYSTEM, and VALOR™ ANKLE FUSION NAIL Systems. Data collected up until the point of death will be included in the final analysis.
- f. Other: A subject may be withdrawn by the Investigator if he/she believes that it is in the best interest of the subject or the IRB/EC may determine that a subject's continued participation in the clinical investigation represents an unacceptable risk to the subject. The Sponsor must be notified immediately if this occurs. All data collected up until the point of withdrawal or IRB/EC determination will be included in the final analysis.

A subject may also be withdrawn if the subject is non-compliant with the clinical investigation procedures or visits, or if a selection criteria violation is noted after the subject received the clinical investigation treatment and it is determined that the subject should be discontinued. All data collected up until the point of withdrawal will be included in the final analysis.

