#### 11.2.4 Safety Analysis

All subjects enrolled in the study will be assessed for safety. AEs and other safety evaluations will be reported as frequencies and rates as appropriate, cumulative over the different follow-up schedules.

Safety endpoints will include all AEs, serious AE (SAE), device related adverse effect (DRAE), procedure related adverse effect (PRAE), serious device-related adverse effect (SDRAE), serious procedure-related adverse effect (SPRAE), unanticipated adverse device effects (UADEs) and type of surgical intervention as a consequence of the AE occurrence. For each type of AE and intervention type, total counts and per subject incident rates with 95% exact binomial confidence intervals will be reported. Counts of AE's will also be reported according to incidence time intervals.

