#### 11.2.5 Additional Analysis

There are two types of fixation, external and internal. External fixation devices are always removed. Survival analysis of time to external fixation removal with Kaplan-Meier survival estimates and corresponding confidence limits will be presented. Internal fixation breakage will be reported as an AE.

Subgroup analysis of patient reported outcome improvement scores (EQ-5D-5L and FAAM) will be conducted for i.) patients with external fixation only, ii.) patients with internal fixation only, iii.) patients with external and/or internal fixation. In addition, subgroup analysis will be conducted by device type (HOFFMANN® LRF SYSTEM, SALVATION™ EXTERNAL FIXATION SYSTEM, SALVATION™ FUSION BOLTS AND BEAMS, SALVATION™ 2 MIDFOOT NAIL, THE SALVATION™ 3DI PLATING SYSTEM, T2® ICF SYSTEM, and VALOR™ ANKLE FUSION NAIL).

**MISSING DATA** For the primary endpoint analysis, subjects that have not experienced the event (i.e., amputation) at the last day of follow-up will be censored in the survival analysis. Patients that dropped out for any reason before their 3-year anniversary will also be censored at the last known date. A sensitivity analysis will be conducted that will exclude patients that dropped out from the study for reasons other than amputation prior to their three-year anniversary.

For the patient reported outcomes (EQ-5D and FAAM), statistical summaries will be computed only for available data. No imputation for missing data will be conducted.

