### 13.2 FORESEEABLE DRAE AND SDRAE

DRAEs, SADREs and incidents which may be expected as part of the surgical interventions include:

- Infection or painful, swollen or inflamed implant site
- Fracture of the implant
- Loosening or dislocation of the implant requiring revision surgery
- Bone resorption or over-production
- Allergic reaction(s) to implant material(s)
- Untoward histological responses possibly involving macrophages and/or fibroblasts
- Migration of particle wear debris possibly resulting in a bodily response
- Embolism
- Abnormal pain and sensations due to the device
- Infection
- Neurologic complication with possible palsy
- Pseudarthrosis

A complete listing of foreseeable ADREs may also be found in the HOFFMANN® LRF SYSTEM, SALVATION™ EXTERNAL FIXATION SYSTEM, SALVATION™ FUSION BOLTS AND BEAMS, SALVATION™ 2 MIDFOOT NAIL, SALVATION™ 3DI PLATING SYSTEM, T2® ICF SYSTEM, and VALOR™ ANKLE FUSION NAIL Systems device labeling and Informed Consent Form.

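### Protocol 9.4 can end outcome collection at an adverse event or at withdrawal, so amputations that follow may go uncounted

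*Protocol*

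**What the plan says.** **Withdrawal.** Protocol 9.4 is permissive: "Subjects may be withdrawn from the clinical investigation for any of the following reasons". Item (d) reads "The discontinuation of a subject's participation due to an AEs that prohibits his/her continued participation must be fully explained", and then "Data collected up until the point of AE will be included in the final analysis". Item (c) treats amputation itself as a withdrawal reason and ends the data there. Item (f) covers withdrawal by the investigator or ethics committee. The closing paragraph adds "A subject may also be withdrawn if the subject is non-compliant with the clinical investigation procedures or visits", together with selection violations found after treatment. Under (f) and the closing paragraph, data stop at withdrawal.

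**Analysis.** Protocol 11.2.5 states "Patients that dropped out for any reason before their 3-year anniversary will also be censored at the last known date". The one sensitivity analysis is this: "A sensitivity analysis will be conducted that will exclude patients that dropped out from the study for reasons other than amputation" before three years.

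**Recovery of data.** Protocol 10.3 and note b of the schedule ask sites to collect late data when a visit is missed. Section 9.4(b) sets contact attempts before a subject is called lost to follow-up. Neither applies to a subject already withdrawn.

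**Safety.** Protocol 11.2.4 states "All subjects enrolled in the study will be assessed for safety", and 8.2 runs AEs through 5 years.

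**SAP.** Enrollment was discontinued with about 42 subjects implanted (4.1). Section 6.3 repeats AE, amputation and non-compliance as withdrawal reasons. All analysis is descriptive (7). The 3-year rate is dropped because nobody reached three years, and amputation frequency per visit and latest status are shown instead (9.1). The 5-year rate is still listed (5.2), but 9.2 gives no analysis for it.

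**The concern.** The study is observational and the devices are already in place, so ending study visits need not end the collection of limb status. Section 13.2 lists infection, implant fracture and "Loosening or dislocation of the implant requiring revision surgery" among the foreseeable events, and section 14 counts amputation as a reoperation. Suppose such an event is severe enough to end participation, and the limb is amputated afterwards. Read literally, 9.4(d) closes the record at the AE, and the amputation is never counted.

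Kaplan-Meier estimation assumes that censored subjects have the same later risk as those still followed. That is doubtful when the reason for censoring may be a step toward the event. At stake are the 3-year comparison with the performance goal and the 5-year rate as the protocol planned them, and today the descriptive amputation counts. If the status was never collected, no later analysis can recover it.

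A separate gap concerns amputees. Ending their data at amputation costs nothing for time to amputation, since the event is already counted. It does lose later AEs and deaths, although safety is to be assessed in everyone enrolled.

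**Working it through.** **Inputs from the documents.** Expected 3-year rate 10%, null value 0.202, one-sided alpha 0.025, 141 evaluable subjects, 200 enrolled, loss allowance 29.5% (Protocol 11.1); about 42 implanted (SAP 4.1). Section 8 prints the goal as 20.5% although 17.2% + 3% = 20.2%, and uses a 95% limit where 11.2.2 uses 97.5%. I use 20.2% and 97.5%.

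**Assumed inputs, not in the documents.** W is the share withdrawn for AE or non-compliance by the horizon: 5% to 29.5%, the top being the whole loss allowance. r is the amputation hazard after withdrawal divided by the hazard of those who stay: 0.5 to 5. Hazards are constant.

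**1. The plan's own figure.** Power = Φ[(p0 − p1 − 1.96√(p0(1 − p0)/n)) / √(p1(1 − p1)/n)] = Φ[(0.102 − 1.96 × 0.03381)/0.02527] = Φ(1.414) = 92.1%. The stated 92% reproduces, and 141/(1 − 0.295) = 200.

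**2. Effect on the 3-year estimate.** Let λ be the hazard of those who stay and μ = −ln(1 − W)/3. The true event-free probability is S = exp(−3(λ + μ)) + ∫₀³ μ exp(−(λ + μ)s − rλ(3 − s)) ds. Solve for λ at the chosen true rate; Kaplan-Meier then estimates 1 − exp(−3λ).

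Example, true rate 10%, W = 29.5%, r = 2: μ = 0.1165 and λ = 0.0305. The two terms are 0.6434 and 0.2566, so S = 0.900. The expected estimate is 1 − exp(−0.0915) = 8.7%.

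The last column sets the true rate at 20.2% and gives the approximate chance of wrongly meeting the goal, Φ[(0.202 − p − 1.96 × 0.03381)/√(p(1 − p)/141)], where p is the expected estimate. For W = 29.5% and r = 2, p = 0.1784 and the argument is −1.32, giving 9.3%.

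| r | Expected estimate, true 10%, W = 5% to 29.5% | Chance of wrongly meeting the goal |
|---|---|---|
| 0.5 | 10.1% to 10.8% | not computed |
| 1 | 10.0% | 2.5% |
| 2 | 9.8% to 8.7% | 3.2% to 9.3% |
| 3 | 9.6% to 7.8% | 3.9% to 20.6% |
| 5 | 9.2% to 6.4% | 5.4% to 49% |

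At 5 years the true rate is 1 − 0.9^(5/3) = 16.1%. The estimate is 15.8% to 14.2% for r = 2, 15.0% to 10.7% for r = 5, and 16.3% to 17.4% for r = 0.5.

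**3. The planned sensitivity analysis.** Excluding non-amputation dropouts gives A/(A + C), with A = [λ/(λ + μ)](1 − exp(−3(λ + μ))) and C = exp(−3(λ + μ)). For a true 10% and W = 29.5% the result is 11.8% (r = 1), 10.3% (r = 2), 9.2% (r = 3) and 7.6% (r = 5). It is too high when there is no problem and too low when the problem is large.

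**4. Break-even.** If 10% of 141 followed subjects are amputated (14.1), the 59 lost would need a rate of (0.202 × 200 − 14.1)/59 = 44.6% to bring the overall rate to the goal.

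**5. Current SAP.** One uncounted amputation among about 42 subjects is 1/42 = 2.4 percentage points.

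**6. Two cut-offs.** Section 9.4(d) ends the data at the AE; 11.2.5 censors at the last known date. For a subject amputated after the AE while still in contact with the site, the first reading drops the event and the second may keep it.

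**The case against.** A reader might infer that the amputation rates are biased low and that the study would wrongly meet its goal. The documents do not support that, for four reasons.

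- **The rule is narrow.** Withdrawal is optional, and only an AE that prohibits participation qualifies. Loosening that needs revision is not in itself a withdrawal ground. Reoperations, including amputation, are collected while a subject is in the study (Protocol 14; schedule note d), and 9.4(d) asks for all available AE information.
- **The direction is not shown.** Bias is zero at equal later risk and upward at lower risk. The link from AE withdrawal to amputation is a clinical inference. Censoring deaths also pushes the other way: for a true cumulative incidence of 10% and assumed 3-year mortality of 5% to 20%, the Kaplan-Meier estimate is 10.3% to 11.1%.
- **Large error rates rest on what is assumed.** Suppose a fraction f of amputations is lost to withdrawal at a true rate of 20.2%. The expected estimate is 1 − 0.798^(1 − f), or 18.4%, 16.5% and 14.6% for f = 10%, 20% and 30%. Simulated false success is then about 7%, 19% and 40% (200 subjects, 29.5% unrelated loss). A low estimate is built in: f = 30% presumes 0.3 × 0.202 × 200 ≈ 12 lost amputations, on top of a loss figure that the protocol offers as the whole allowance.
- **The SAP has overtaken the test.** It has no 3-year rate, no hypothesis test and no specified 5-year analysis.

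All four stand, and they limit the claim to possible bias. They do not remove the gap. Status after withdrawal is still not sought, and the exclusion analysis drops the same subjects. SAP Table 1.1 would show AE discontinuations by device, and 10.2 promises serious AE narratives. But Table 1.1 has no row for non-compliance and gives no limb status at exit.

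**Conclusion.** The point holds in limited form. Followed as written, 9.4 and 11.2.5 can lose amputations that occur after withdrawal for an AE, non-compliance or a selection violation, and the planned sensitivity analysis does not repair this. The protocol's Kaplan-Meier rates may be biased low if withdrawn subjects carry higher later risk. The documents give neither W nor r, so there is no single corrected figure. The ranges above illustrate the 200-subject design under constant hazards and are not properties of the current analysis.

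For the study as it now stands, the consequence is possible under-counting in the per-visit amputation frequencies and latest status, at about 2.4 percentage points per missed case. Separately, ending data at amputation loses later AEs and deaths among amputees; that conclusion does not depend on W, r or the direction of bias. This is a cheap improvement, not a flaw that overturns a result.

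**What to change.** **Protocol.** In 9.4(c), (d), (f) and the closing paragraph, separate stopping study visits from leaving the study. Where consent allows, ascertain amputation status, vital status and serious AEs by call or record review, for as long as the study still follows subjects. Reword the data cut-off in 9.4(d) so that it agrees with the last known date in 11.2.5.

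**SAP.** Before data lock, make one status check on subjects already withdrawn. If that is not possible, list the AE and non-compliance withdrawals with AE type and last known limb status, and state that amputations may be under-counted.

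**If a rate is ever estimated.** Replace the exclusion sensitivity analysis with a worst-case or tipping-point analysis over the withdrawn subjects.

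**Cost.** An amendment with consent wording, and a brief status check for a few subjects. The listing alternative needs no new data collection.

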## 10 Clinical Investigation Evaluations, Procedures and Assessments

### 10.1 METHODS OF ASSIGNING SUBJECTS

No specific methods (e.g. randomization, blinding, or stratification) for assigning subjects are used in this CIP. Consecutive subjects at each site meeting all the eligibility criteria will be enrolled in this clinical investigation.

### 10.2 PROCEDURES

Subjects in the clinical investigation will undergo placement of the HOFFMANN® LRF SYSTEM, SALVATION™ EXTERNAL FIXATION SYSTEM, SALVATION™ FUSION BOLTS AND BEAMS, SALVATION™ 2 MIDFOOT NAIL, SALVATION™ 3DI PLATING SYSTEM, T2® ICF SYSTEM, and VALOR™ ANKLE FUSION NAIL Systems. Please see the approved IFUs and Surgical Technique Manuals for a detailed description of the medical device(s) and instrumentation, intended use information and associated risks. Any additional clinically indicated procedures are permitted as deemed necessary by the clinical investigator.

### 10.3 FOLLOW-UP EVALUATIONS

Subjects in this clinical investigation will be evaluated at Pre-Operative, Operative/Discharge, and at 6 Months and yearly through 5 years after the index procedure. The follow-up evaluations will include assessment of device-related adverse events/incidents, evaluation per EQ-5D-5L and FAAM scores as well as surgeon surveys radiographic assessment of deformity correction, and fusion/consolidation time. Demonstration of bone consolidation in correct alignment will be measured by Investigator assessment through 1 Year. Investigators should consider weight-

bearing, pain and imaging when clinically assessing bone consolidation. See the section below for visit windows and a list of assessments to be performed at each visit.

Investigative site personnel will contact subjects prior to their scheduled follow-up evaluations to encourage compliance with clinical investigation visits and participation.

If a subject misses a visit and is outside of the visit window, every effort should be made to collect data instead of noting the visit as missed.

#### 10.4 SCHEDULE OF EVENTS

Assessment	Pre-Operative	Operative/ Discharge	6 months a, b (+/-3 months)	1 Year a, b (+/-6 months)	2-5 years a, b (+/-6 months)	Study Close
Informed Consent	X					
Inclusion/Exclusion	X					
Demographics & Medical History	X					
Disease State Pre-Op	X					
EQ-5D-5L	X		X	X	X	
FAAM	X		X	X	X	
Surgical Procedure		X				
Investigator Assessment			X	X	X	
Adverse Event Assessment		X	X	X	X	
Staged Operative Information d						
Surgical Intervention d						
Subject Disposition c						X

a. Follow-up visit schedule to reflect Institutions' Standard of Care practices.  
 b. If the subject missed a visit and is outside of visit window, every effort should be made to collect data instead of noting visit as missed.  
 c. Subject Disposition assessment will occur at any time point for subject withdrawal prior to the completion of the clinical investigation.  
 d. These are not scheduled time point events but will be observed throughout the study participation

Table 10.4.1 Schedule of Events

## 11 Statistical Considerations

In general, the statistical analysis of will consider the combined outcome of all the devices under investigation. The population of the study will consist of all patients implanted with one or more of the devices listed Table 6.1. Subgroup analysis will be conducted for each device and device groups (i.e., devices for internal fixation only). The study required a sample size of 141 patients to provide at least 80% statistical power to reject the hypothesis that the 3-year amputation rate is less than the PG with a significance  $\alpha=0.05$ . The final statistical analysis will occur after all subjects have completed their 3-year anniversary. Secondary effectiveness endpoints include the total and component scores of the EQ-5D-5L and FAAM. Assessment of patient-reported outcome measure (PROM) improvement will be assessed at each planned study visit. The safety endpoints will include AEs, complications and secondary surgical intervention experienced by the patients. The device- and procedure- relatedness and severity of the safety endpoints will be assessed. The clinical and radiographic surgeon assessment of fusion and consolidation at 5 years will also be assessed.

Data will be captured via the EDC system. The data will be summarized descriptively at each pre-determined clinical visit. Quantitative factors will be summarized with mean, median, standard deviation and range minimum, maximum. Frequency and percentage will be computed for categorical factors. Survival analysis will be conducted to analyze time-to-event variables. Subjects without events will be censored at their last known event-free time point. Survival curves will be constructed using Kaplan-Meier estimates with confidence limits. A significance level ( $\alpha$ ) is 0.05 will be used for all tests of hypotheses

All statistical analysis will be performed using SAS version 9.4 or higher. A Statistical Analysis Plan (SAP) that contain the details of the analysis will be developed and finalized prior to the first anniversary of the first patient enrolled in the study.

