## 6 Introduction

Stryker introduced multiple devices to treat deformity in the neuropathic patient (lack of sensation with the 10 gram Semmes Weinstein monofilament) population. All of the devices have been cleared by the FDA. See below for the list of devices, dates of clearance, and FDA 510K numbers.

Device Name	Date of Clearance	510K Number
HOFFMANN® LRF SYSTEM	01Feb2021	K203568
SALVATION™ EXTERNAL FIXATION SYSTEM	06Jun2018	K180832
SALVATION™ FUSION BOLTS AND BEAMS	21Mar2014	K140741
SALVATION™ 2 MIDFOOT NAIL	11Jul2018	K180024
SALVATION™ 3DI PLATING SYSTEM	22May2014	K140792
SALVATION™ OSTEOPENIC SCREW	14May2014	K140408
T2® ICF SYSTEM	20Mar2020	K193366
VALOR™ ANKLE FUSION NAIL	22Oct2014	K142602

Table 6.1 Study Device FDA 510K Clearance Information

The primary outcome measure of this study will compare the pooled cumulative 3-year amputation rate derived from a Kaplan-Meier survival analysis to a performance goal derived from a literature-based source. Descriptive analyses will then compare survival curves in patients for specific devices over the entire 5-year follow-up period. Secondary endpoints include improvements in patient-reported pain, function, and social interaction for quality of life from pre-op through each annual visit as assessed by the EQ-5D-5L and the FAAM and its component scores. As well as investigator assessment of the implant including radiographic assessment of deformity correction, and fusion/consolidation time through 1 Year

The outcome measures collected in this study will be analyzed and reported as required for local, regional, and country requirements (i.e., regulatory authorities and notified bodies).

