6.6 Sample Size

The study required a sample size of 141 patients to provide at least 80% statistical power to reject the hypothesis that the 3-year amputation rate is less than the PG with a significance $\alpha=0.05$. However, this sample size requirement was not met at study discontinuation.

7 General Analysis Considerations

Data will be summarized for each of the devices listed in **Table 1**. Because the study was prematurely terminated, all analysis will be descriptive only. All analyses will be done to summarize all available data. No statistical hypothesis testing will be implemented.

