10.1 Adverse Events

The safety of each device will be summarized in the final report. The overall summary of adverse events will be presented for each device. Total events, patient counts and percentages of adverse events for each device will be summarized for the following factors:

- i.) Procedure-Related Adverse Event / Incident.
- ii.) Device-Related Adverse Event / Incident
- iii.) Device Failure
- iv.) Serious Adverse Event (SAE)
- v.) Hospitalization SAE Outcome
- vi.) Treatment Required for the AE

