	ORTHOLOC™ 3Di Midfoot/Flatfo ot	SALVATION™ External Fixation (N=xx)	SALVATION™ Fusion Bolts and Beams (N=xx)	SALVATION™ MIDFOOT NAIL (N=xx)	VALOR™ Nail (N=xx)
Indications for Use					
Post traumatic	xx(xx.xx%)	xx(xx.xx%)	xx(xx.xx%)	xx(xx.xx%)	xx(xx.xx%)
Arthritis	xx(xx.xx%)	xx(xx.xx%)	xx(xx.xx%)	xx(xx.xx%)	xx(xx.xx%)
Fracture	xx(xx.xx%)	xx(xx.xx%)	xx(xx.xx%)	xx(xx.xx%)	xx(xx.xx%)
Fusion	xx(xx.xx%)	xx(xx.xx%)	xx(xx.xx%)	xx(xx.xx%)	xx(xx.xx%)
Reconstruction/Correction	xx(xx.xx%)	xx(xx.xx%)	xx(xx.xx%)	xx(xx.xx%)	xx(xx.xx%)
Revision procedure	xx(xx.xx%)	xx(xx.xx%)	xx(xx.xx%)	xx(xx.xx%)	xx(xx.xx%)
Instability	xx(xx.xx%)	xx(xx.xx%)	xx(xx.xx%)	xx(xx.xx%)	xx(xx.xx%)
Skeletal defect	xx(xx.xx%)	xx(xx.xx%)	xx(xx.xx%)	xx(xx.xx%)	xx(xx.xx%)
Previous Surgery to Index procedure					
No	xx(xx.xx%)	xx(xx.xx%)	xx(xx.xx%)	xx(xx.xx%)	xx(xx.xx%)
Yes	xx(xx.xx%)	xx(xx.xx%)	xx(xx.xx%)	xx(xx.xx%)	xx(xx.xx%)
Operative Side					
Left	xx(xx.xx%)	xx(xx.xx%)	xx(xx.xx%)	xx(xx.xx%)	xx(xx.xx%)
Right	xx(xx.xx%)	xx(xx.xx%)	xx(xx.xx%)	xx(xx.xx%)	xx(xx.xx%)
Wright Biologics use					
No	xx(xx.xx%)	xx(xx.xx%)	xx(xx.xx%)	xx(xx.xx%)	xx(xx.xx%)
Yes	xx(xx.xx%)	xx(xx.xx%)	xx(xx.xx%)	xx(xx.xx%)	xx(xx.xx%)
Intra-operative complication					
No	xx(xx.xx%)	xx(xx.xx%)	xx(xx.xx%)	xx(xx.xx%)	xx(xx.xx%)
Yes	xx(xx.xx%)	xx(xx.xx%)	xx(xx.xx%)	xx(xx.xx%)	xx(xx.xx%)

Table 3.1 EQ-5D Score

		Baseline			Final Visit			1 Yr. Visit				
	n	Mean ± SD	min,max	95% CI	n	Mean ± SD	min,max	95% CI	n	Mean ± SD	min,max	95% CI
SALVATION™ Fusion Bolts and Beams												
EQ-VAS Score	xx	xxx.x ± xx.x	xx.x , xx.x	xx.x, xx.x	xx	xx.x ± xx.x	xx.x , xx.x	xx.x, xx.x	xx	xx.x ± xx.x	xx.x , xx.x	xx.x, xx.x
EQ-5D Index	xx	xxx.x ± xx.x	xx.x , xx.x	xx.x, xx.x	xx	xx.x ± xx.x	xx.x , xx.x	xx.x, xx.x	xx	xx.x ± xx.x	xx.x , xx.x	xx.x, xx.x
Change from Baseline												
EQ-VAS Score	xx	xxx.x ± xx.x	xx.x , xx.x	xx.x, xx.x	xx	xx.x ± xx.x	xx.x , xx.x	xx.x, xx.x	xx	xx.x ± xx.x	xx.x , xx.x	xx.x, xx.x
EQ-5D Index	xx	xxx.x ± xx.x	xx.x , xx.x	xx.x, xx.x	xx	xx.x ± xx.x	xx.x , xx.x	xx.x, xx.x	xx	xx.x ± xx.x	xx.x , xx.x	xx.x, xx.x
SALVATION™ MIDFOOT NAIL												
EQ-VAS Score	xx	xxx.x ± xx.x	xx.x , xx.x	xx.x, xx.x	xx	xx.x ± xx.x	xx.x , xx.x	xx.x, xx.x	xx	xx.x ± xx.x	xx.x , xx.x	xx.x, xx.x
EQ-5D Index	xx	xxx.x ± xx.x	xx.x , xx.x	xx.x, xx.x	xx	xx.x ± xx.x	xx.x , xx.x	xx.x, xx.x	xx	xx.x ± xx.x	xx.x , xx.x	xx.x, xx.x
Change from Baseline												

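### The SAP's outcome and adverse-event shells give no pooled result, leave out up to three of the seven eligible systems, and state no rule for subjects with combined systems

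*Protocol*

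**What the plan says.** Protocol 9.1c admits a subject who is "intended to be treated for deformity with the one or a combination of the below Systems", followed by seven names. The point of enrolment (9.3d), the primary endpoint (8.1) and the subgroup list (11.2.5) name the same seven. On timing, 9.3 adds: "The subject is enrolled in the study once they have received the study device".

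Protocol section 11 makes the combined outcome of all devices the general basis of analysis, with device subgroups in addition. Its population sentence points to a different list: "The population of the study will consist of all patients implanted with one or more of the devices listed Table 6.1". Table 6.1 has eight rows; the extra one is "SALVATION™ OSTEOPENIC SCREW".

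The SAP is descriptive only. Section 7 says: "Data will be summarized for each of the devices listed in Table 1". That table repeats the eight rows. Section 7.3 rules out subgroup analysis. Section 9.1 drops the 3-year rate because no subject reached three years, and presents amputation counts by visit and status at latest follow-up instead. For safety, section 10.1 says: "Total events, patient counts and percentages of adverse events for each device will be summarized for the following factors". The shells that carry this out are in SAP 15.1. One column of Table 2.1 is headed "ORTHOLOC™ 3Di Midfoot/Flatfo ot".

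**The concern.** With no hypothesis test left, the tables are the study's result. Section 9.1 puts amputation counts and latest status in place of the primary endpoint, so a reader will look first for the number of amputations among all implanted subjects. The visible shells have no place for that number, and some eligible subjects have no place in them either. The pooled figure cannot be rebuilt by adding columns: some systems are missing, and it is not stated whether the columns overlap. Two programmers working from the same data could produce different denominators and percentages, both consistent with the SAP.

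**Working it through.** **Step 1: device lists side by side.** The reference is Protocol 9.1c.

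| Place | Devices | Difference from 9.1c |
|---|---|---|
| Protocol synopsis, 8.1, 9.3d, 11.2.5; SAP 5.1, 6.2 | 7 | none |
| Protocol Table 6.1; SAP Table 1 | 8 | Osteopenic Screw added |
| SAP Table 1.1 | 7 | none |
| SAP Tables 1.3, 1.4, 1.7, 3.1, 3.2, 3.4, 4.1 | 5 | HOFFMANN LRF and T2 ICF absent |
| SAP Table 2.1 | 5 | same two absent; ORTHOLOC heading where Table 1.7 has SALVATION 3Di Plating |
| SAP Table 3.3 | 4 | same two absent, and SALVATION External Fixation |

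No visible shell has a place for the Osteopenic Screw, so SAP 7 cannot be followed literally for its own Table 1.

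**Step 2: where all subjects appear together.** Table 1.4 has an all-subjects row, and Tables 1.5 and 1.6 cover all subjects. Tables 3.1, 3.2, 3.3, 3.4 and 4.1 have no such group. The total line in Table 4.1 is a row within each device column, not a column across devices.

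**Step 3: follow one amputation.** The only visible shell with an amputation row is Table 3.3, under current status. Its blocks are Fusion Bolts and Beams, Midfoot Nail, 3Di Plating and VALOR. A subject treated only with HOFFMANN LRF, T2 ICF or SALVATION External Fixation is eligible and belongs to the ITT set of SAP 7.2, but has no cell there. That is 7 − 4 = 3 eligible systems.

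**Step 4: combinations.** Neither document says whether a combination subject is counted under every system, under a main system, or in a separate group. Suppose a share s of the 42 had two systems and were counted under both. With all seven systems shown, the columns would total 42 × (1 + s):

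- s = 0: 42
- s = 0.25: 52.5, about 53
- s = 0.50: 63
- s = 1: 84

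The pooled denominator is 42 in every case. The share is not in the documents, so this is a range, not an estimate.

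**Step 5: how coarse the columns are.** An even split, assumed for illustration, gives 42 / 7 = 6 subjects per system. One event then moves a column by 1/6 = 16.7 percentage points, against 1/42 = 2.4 points in a pooled group.

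**Step 6: does the device list touch the sample size?** The Protocol 11.1 inputs are null 0.202, true rate 0.10, one-sided α = 0.025 and N = 141. Power = Φ{[(0.202 − 0.10)√141 − 1.96√(0.202 × 0.798)] / √(0.10 × 0.90)} = Φ(1.414) = 92.1%, which matches the stated 92%. Also 141 / (1 − 0.295) = 200. No device list enters either figure, so reconciling the lists changes neither.

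**The case against.** The best defence is that these are unfilled shells for a stopped, descriptive study. Some details look like template carry-over: Table 1.4 shows 114 subjects against about 42 implanted, and the ORTHOLOC heading appears nowhere else. HOFFMANN LRF and T2 ICF joined the Protocol in version 2, and perhaps no subject received them. SAP 8.1 promises disposition overall as well as by device, the listings will show every subject, and each serious event gets a narrative. The layouts of Tables 4.2 and 4.3 are not in the available text, so nothing is claimed about them. All of this lowers the stakes. It does not supply a pooled outcome, adverse-event or amputation table, and the SAP does not say that any system went unused.

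Three stronger readings are tempting, and the documents do not support them.

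- **That combination subjects are counted under every system.** No counting rule is stated, so this is an inference. The defect is the missing rule.
- **That the analysis population differs materially from the eligible one.** Protocol 9.3d requires one of the seven systems, so a subject with only the screw should not be enrolled, and SAP 4.1 covers subjects who were enrolled and implanted. The documents do not say whether the screw is a component of a listed system.
- **That adverse events are credited to devices that did not cause them.** Table 4.1 counts events among recipients of a device and has separate device-related and procedure-related rows. A count by device received is not a causal claim.

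**Conclusion.** The point stands as a reporting defect. Tables 3.1 to 4.1, as shown, give no result for all subjects, although Protocol 11 makes the combined outcome the general analysis. Two eligible systems are missing from every visible by-device shell except Table 1.1. A third is missing from Table 3.3, the only visible home for amputation status. Combinations are allowed without a rule for placing them, so column totals could lie anywhere from 42 to 84 if no subject had more than two systems and all seven were shown. The Osteopenic Screw and ORTHOLOC mismatches are close to clerical. No power figure or hypothesis test is affected. How many subjects lack a cell depends on which systems were implanted, and the documents do not give that.

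**What to change.** 1. In Tables 3.1 to 4.1, add an all-subjects group that counts each subject and each event once. This is the essential change.
2. Show all seven systems of Protocol 9.1c in every by-device shell. If a system was not used, say so with a zero denominator or a footnote.
3. State that per-device columns are by device received and may overlap, so they need not add to the number of subjects. Alternatively, define a combination group. That avoids overlap but makes already small groups smaller.
4. Refer to the seven-system list in Protocol 11 and SAP 7 instead of the clearance tables, which can stay as regulatory information.
5. Correct the Table 2.1 heading to SALVATION 3Di Plating.
6. Attribute a device-related event to a particular system only if the adverse-event form records which one. Protocol 13.1 asks only about the study device or the implant procedure.

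The cost is wording and a few more table columns. Apart from item 6, no new data are needed.
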